8.1.3.3.1. Management of patients with NS5A resistance variants

Once HCV infection is confirmed, patients will have their HCV genotype reconfirmed. Patients with Genotype 1a and Genotype 1 with an unknown subtype will have baseline NS5A drug resistance assay testing. This will be checked at start of treatment. If patients have polymorphisms at positions M28, Q30, L31, and/or Y93, treatment with Zepatier will be extended to 16 weeks, rather than 12 weeks, and renally-adjusted Ribavirin at the clinician's discretion will be initiated, and continued for the remainder of therapy (until the 16 week mark). Such a strategy will provide optimal treatment, without delaying therapy prior to receipt of results of NS5A drug resistant testing. Under such a scenario, all of the study procedures referenced above and below will be extended by 4 weeks. Any patient (male or female) receiving ribavirin as part of the first- or second-line regimen will be required to use two methods of birth control while on Ribavirin therapy, with continuing two forms of birth control for up to 6 months after the last dose of the study drug.

8.1.3.3.2. Management of patients with positive HBV Core Antibody

For patients with a positive HBV Core Antibody, HBV-DNA levels will be checked every 6 weeks while on Zepatier and LFTs will be closely monitored. HBV therapy may be considered the transplant team as medically appropriate.

8.1.3.4. Visit 2: Post-Heart Transplant (day 10 ± 2 day)

Visit #2 should occur two weeks (10 ± 2 days) after the subject's heart transplant and coincide with the subject's regularly scheduled post-transplant follow-up visit. The staff will call the subject 1-2 days before the visit. During this phone call, the research staff will remind the subject where to go for the study visit, to take their routine and study medications as they usually would prior to the visits.

The subject will arrive at the study site outpatient clinic. The following procedures and activities will be performed:

- Assess for Adverse Events
- Obtain medication data
- Research Phlebotomy (See Section 8.2.1 for complete list)
- Pill count and drug diary assessed for adherence
- Schedule appointments for follow-up visits

8.1.3.5. Visit 3: Post-Heart Transplant (day 21 ± 3 days)

Visit #3 should occur three weeks (21 ± 3 days) after the patient's heart transplant and coincide with the subject's regularly scheduled post-transplant follow-up visit. The staff will call the subject 1-2 days before the visit. During this phone call, the research staff will remind the subject where to go for the study visit, to take their routine and study medications as they usually would prior to the visits.

The subject will arrive at the study site outpatient clinic. The following procedures and activities will be performed:

- Assess for Adverse Events
- Obtain medication data
- Research Phlebotomy (See Section 8.2.1 for complete list)
- Pill count and drug diary assessed for adherence
- Schedule appointments for follow-up visits

8.1.3.6. Visit 4 Post-Heart Transplant (day 28 ± 3 days)

Visit #4 should occur 4 weeks (28 ± 2 days) after the subject's heart transplant and coincide with the subject's regularly scheduled post-transplant follow-up visit. The staff will call the subject 1-2 days before the visit. During this phone call, the research staff will remind the subject where to go for the study visit, to take their routine and study medications as they usually would prior to the visits.

The subject will arrive at the study site outpatient clinic. The following procedures and activities will be performed:

- Assess for Adverse Events
- Obtain medication data
- Research Phlebotomy (See Section 8.2.1 for complete list)
- Health Status Questionnaire (RAND-36) (to assess changes in health status from pre- to post-transplant)
- Pill count and drug diary assessed for adherence

- Replenish study drug
- Schedule appointments for the follow-up visits

HCV Non-Transmission

It is possible that a subject may not develop chronic HCV infection, either due to non-transmission or spontaneous clearance of HCV by week 4 (defined as an initial positive HCV RNA and subsequent undetectable HCV RNA without treatment). If a subject has an undetectable HCV RNA based on the week 4 HCV RNA, a repeat HCV RNA will be checked at week 8 to ensure non-infection with HCV, rather than a false-negative HCV RNA. If the week 8 HCV RNA confirms lack of infection (undetectable week 8 HCV RNA), then no further treatment will be needed. Subjects will be assessed at a study visit and HCV RNA levels re-checked at week 16 and 28 post-heart transplantation. Should any subject spontaneously clear HCV without treatment, another subject will replace them in order to meet our planned treatment sample size.

8.1.3.7. Visits 5-7: Post-Heart Transplant (day 42±7, day 56±7, day 70±7)

Visit #5 should occur 6 weeks (42±7 days) after the subject's heart transplant and will coincide with the subject's regularly scheduled post-transplant follow-up visit. Visit #6 should occur 8 weeks (56±7 days) after the subject's heart transplant and will immediately follow the subject's regularly scheduled post-transplant follow-up visit. Visit #7 should occur 10 weeks (70±7 days) after the subject's heart transplant and will immediately follow the subject's regularly scheduled post-transplant follow-up visit.

For both visits, the staff will call the subject 1-2 days before the visit to remind subject of visit. During this phone call, the research staff will remind the subject where to go for the study visit, to take their routine and study medications as they usually would prior to the visits.

The following procedures and activities will be performed:

- Assess for Adverse Events
- Obtain medication data
- Research Phlebotomy (See Section 8.2.1 for complete list)
- Replenish study drug
- Pill count and drug diary assessed for adherence
- Schedule appointments for follow-up visits

The staff will replenish the subject's 28-day supply of the Zepatier study drug sometime during visits #5 & 6, depending on when the subject began treatment.

8.1.3.8. Visits 8 & 9: Post-Heart Transplant (day 87 + 7, day 115 + 14)

Visit #8 should occur 12 weeks (87 + 7 days) after the subject's heart transplant and will coincide with the subject's regularly scheduled post-transplant follow-up visit. Visit #9 should occur 16 weeks (115 + 14 days) after the subject's heart transplant and will immediately follow the subject's regularly scheduled post-transplant follow-up visit.

Midway between these study visits, subjects will be phoned in order to ensure drug adherence, if necessary

For both visits, the staff will call the subject 1-2 days before the visit to remind subject of visit. During this phone call, the research staff will remind the subject where to go for the study visit, to take their routine and study medications as they usually would prior to the visits.

The following procedures and activities will be performed:

- Assess for Adverse Events
- Obtain medication data
- Research Phlebotomy (See Section 8.2.1 for complete list)
 - Note: Timing for HCV RNA viral load, post treatment, should, as best possible, follow the important data collection points post treatment. These are as follows:
 - Post-treatment: This should occur after the subject has completed treatment of the study drug.
 - SVR 4: This should occur ~4 weeks after the subject has completed treatment.
 - SVR 8: This should occur ~ 8 weeks after the subject has completed treatment.
 - SVR 12: This should occur ~12 weeks after the subject has completed treatment.
 - SVR 24: This should occur ~24 weeks after the subject has completed treatment.
- Health Status Questionnaire (RAND-36) (to assess changes in health status from pre- to post-transplant)
- Pill count and drug diary assessed for adherence
- Replenish study drug
 - Note: The staff will replenish the subject's supply of the Zepatier study drug between visits 7 & 8, if necessary. This is based on management of patients NS5A resistance variants, in any were are present . The staff will also remind the subject how to take the medication, for those subjects still on study medication.

8.1.3.9. Visit 10 Post-Heart Transplant (day 171 ±7 days)

Visit #10 should occur 24 weeks (171 ±7 days) after the subject's heart transplant and will coincide with the subject's regularly scheduled post-transplant follow-up visit.

For this visit, the staff will call the subject 1-2 days before the visit. During this phone call, the research staff will remind the subject where to go for the study visit, to take their routine and study medications as they usually would prior to the visits.

The following procedures and activities must be performed:

- Assess for Adverse Events
- Research Phlebotomy (See Section 8.2.1 for complete list)
 - Note: Timing for HCV RNA viral load, post treatment, should, as best possible, follow the important data collection points post treatment. These are as follows:
 - Post-treatment: This should occur after the subject has completed treatment of the study drug.
 - SVR 4: This should occur ~4 weeks after the subject has completed treatment.
 - SVR 8: This should occur ~ 8 weeks after the subject has completed treatment.
 - SVR 12: This should occur ~12 weeks after the subject has completed treatment.
 - SVR 24: This should occur ~24 weeks after the subject has completed treatment.
- Health Status Questionnaire (RAND-36) (to assess changes in health status from pre- to post-transplant)

8.1.3.10. Visit 11 Post-Heart Transplant (day 365 ±14)

Visit #10 should occur 52 weeks (365 ±14 days) after the subject's heart transplant and will coincide with the subject's regularly scheduled post-transplant follow-up visit.

For this visit, the staff will call the subject 1-2 days before the visit. During this phone call, the research staff will remind the subject where to go for the study visit, to take their routine and study medications as they usually would prior to the visits.

The following procedures and activities must be performed:

- Assess for Adverse Events
- Research Phlebotomy (See Section 8.2.1 for complete list)
- Health Status Questionnaire (RAND-36) (to assess changes in health status from pre- to post-transplant)

The Research Staff should fill out the **Study Closeout Form**. This form must be signed by the principal investigator.

8.1.3.11. Additional Visits

Additional visits will only be necessary in the case of treatment failures. If treatment failure occurs, subjects will be treated with Zepatier and two other hepatitis C medications, Sofosbuvir (Sovaldi), and Ribavirin for an additional 12 weeks. All study and lab visits will be repeated during this secondary treatment period. NS5A resistance (RAV) testing will be checked again (a second time) prior to initiating second-line therapy.

8.1.4. Future research

Subjects will also be approached to provide optional blood sample for testing of viral kinetics (HCV RNA), donor and recipient IL-28B polymorphisms, and alloimmune responses (T- and B-cell function). Samples will be stored in a locked freezer, using encrypted patient IDs.

De-identified samples from subjects may be sent to other investigators for their research. These samples may include information such as sex, age, health history, or ethnicity. These samples will not be sold. Some future studies may need health information (such as smoking history or present health status) that may require contacting the subject to obtain.

8.2. Study schedule of procedures

8.2.1. Visits, lab testing, and other clinical testing

See next page for table.

Transplanting HCV Hearts into HCV Negative Heart Recipients

Protocol V.2.0. 06/09/2017

		Visit Schedule			Research Visit Activities				Research Labs						Standard of Care						
Week(s) post-KT	Day(s) post-KT	Visit	Study Visits	Lab-Only	Informed Consent	Assess Adverse Events	Current Medications	RAND-36 Health Status Questionnaire	HBV DNA HIV AB & LFTs	HBV Core Antibody	Urine Preg Test	Urine Protein/Creatinine Ratio	HCV RNA	Viral Kinetics (optional)♦	NS5A Resistance	Genotyping	Vitals & Physical Exam	Surveillance biopsy	CMP*	CBC	Tacrolimus
Screening					✓	✓	✓		✓	✓	✓		✓			✓			✓		
1 (Begin treatment)	3 ± 1 day	V1	✓			✓	✓		✓	✓			✓	✓	✓	✓	✓	✓	✓	✓	✓
1	7 ± 1 day			✓			✓						✓	✓					✓	✓	✓
2	10 ± 1 day	V2	✓			✓	✓						✓	✓				✓	✓	✓	✓
2	14 ± 1 day			✓			✓						✓	✓				¥	✓	✓	✓
3	21 ± 3 day	V3	✓			✓	✓						✓	✓				✓	✓	✓	✓
4	28 ± 3 day	V4	✓			✓	✓	✓					✓	✓	✓			✓	✓	✓	✓
6	42 ± 7 day	V5	✓			✓	✓			✓			✓	✓				✓	✓	✓	✓
8	56 ± 7 day	V6	✓			✓	✓						✓	✓				✓	✓	✓	✓
10	70 ± 7 day	V7	✓			✓	✓							✓				✓	✓	✓	✓
12	84 ± 7 day	V8	✓			✓	✓			✓			✓	✓	✓			✓	✓	✓	✓
13 (End treatment)†	91 ± 7 day			✓			✓							✓							
16 (SVR 4)†	112 ± 14 day	V9	✓ †			✓	✓	✓					✓	✓			✓ †	✓	✓	✓	✓
20 (SVR 8)	140 ± 7 day			✓									✓	✓				✓	✓	✓	✓
24 (SVR 12)	168 ± 14 day	V10	✓			✓		✓					✓	✓	✓			✓	✓	✓	✓
28†	196 ± 7 day			✓										✓				✓	✓	✓	✓
32	224 ± 7 day			✓										✓				✓	✓	✓	✓
36 (SVR 24)	252 ± 7 day			✓									✓	✓	✓			✓	✓	✓	✓
40	280 ± 14 day			✓										✓				✓	✓	✓	✓
52	365 ± 14 day	V11	✓			✓							✓	✓	✓			✓	✓	✓	✓

* CMP=comprehensive metabolic panel which includes basic metabolic panel and liver function tests

Viral Kinetics testing can be done anytime there is a standard of care blood draw. Only if HRV Core Antibodies are positive.

If patients require the 16 weeks of therapy, the last 4 weeks would be the same as weeks 9-12 of

◆ Viral Kinetics testing can be done anytime there is a standard of care blood draw.

■ Only if HBV Core Antibodies are positive

8.2.2. Blood sampling volumes

Maximum Post-Transplant Blood Draw Totals								
Week Post-KT	CBC	CMP	Tacrolimus	HBV Core Antibody	HCV RNA	Viral Kinetics (optional)♦	NS5A Resistance	Blood Draw Total
1	4	4.5	4	4	6	6	2	28.5
1	4	4.5	4	0	6	6	0	24.5
2	4	4.5	4	0	6	6	0	24.5
2	4	4.5	4	0	6	6	0	24.5
3	4	4.5	4	0	6	6	0	24.5
4	4	4.5	4	0	6	6	0	18.5
6	4	4.5	4	4	6	6	0	24.5
8	4	4.5	4	0	6	6	0	24.5
10	4	4.5	4	0	0	6	0	18.5
12	4	4.5	4	4	6	6	0	28.5
16	4	4.5	4	0	6	6	0	24.5
20	4	4.5	4	0	6	6	0	24.5
24	4	4.5	4	0	6	6	0	24.5
28	4	4.5	4	0	0	6	0	18.5
36	4	4.5	4	0	6	6	0	24.5
40	4	4.5	4	0	0	6	0	18.5
52	4	4.5	4	0	6	6	0	24.5
Total	68	76.5	68	0	84	102	2	400.5

♦ There may be additional blood draws due to optional Viral Kinetics lab testing increasing the total sample volume.

8.3. Subject retention and drug adherence

We will enforce subject retention in several ways. We will record extensive contact information for each subject at their enrollment in the trial. This will include home, work, and cellular telephone numbers. The research staff will call before each study visit to remind the subject to attend. We will also obtain contact information of a family member or friend so that we can contact him/her if the subject does not answer his/her regular phone number.

An adequate record of receipt, distribution, and return of all study drugs must be kept. Subject adherence with the treatment and protocol includes willingness to comply with all aspects of the protocol, and to have blood collected for all safety evaluations.

The research staff and physician will explain the importance of adherence with the study protocol at each subject contact. If a subject fails to comply with a study visit, the staff will contact him or her by telephone. If this fails, the staff will send two certified express letters one week apart, to request follow-up.

We have considered how to minimize non-adherence with therapy. We will strongly emphasize the importance of complying with the study drug treatment. Nonetheless, we will perform pill counts at visits and record episodes when medication is withheld for any reason. If a subject has a serious adverse event (SAE) (whether related to study drugs or not), we will continue to follow-up with the subject for study assessments to assist with safety monitoring and to avoid the problems introduced by missing data. The inclusion of such follow-up data

will allow for analysis by intention-to-treat. If a study subject withdraws consent, he/she will no longer be followed.

9 CHAPTER 6: ASSESSMENT OF EFFICACY AND OUTCOME MEASURES

9.1. Assessments of Efficacy

The primary aims of the study are to determine sustained virologic response rates (SVR) of open-label Zepatier administered to HCV-negative patients with heart failure who receive a heart transplant from a genotype 1 or 4 HCV-positive donor, leading to post-transplant de-novo HCV infection.

9.1.1. Sustained Virologic Response (SVR)

SVR will be based on the standard definition of SVR-12, defined as an undetectable HCV RNA in a subject's serum 12 weeks after completing treatment for HCV (12 weeks after the subject takes the last dose of Zepatier).

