	
 • Major chronic disabling illness (e.g. lupus, severe arthritis, neurologic diseases, previous stroke with profound residual). • Pulmonary infarction within the past 6 weeks • Severe pulmonary hypertension as evidenced by a fixed pulmonary vascular resistance of greater than 4 Wood units on appropriate medical therapy. • Patient refusal to receive blood products or transfusions during heart transplant surgery. • Severe chronic obstructive pulmonary disease • Current clinical sepsis. • Symptomatic or severe vascular disease. • Chronic Kidney Disease Stage IV, GFR < 30 • History of Mantle radiation. • Asymptomatic renal cell carcinoma <1 year from curative treatment. • Symptomatic renal cell carcinoma <5 years from curative treatment. • Prostate cancer <2 years from curative treatment. • Uterine or cervical cancer <2 years from curative treatment. • Any other cancer other than the above including malignant melanoma, < 5 years from treatment apart from other skin malignancies.
Study design	
Open-labelled pilot clinical trial of Zepatier (MK-5172 and MK-8742/Grazoprevir + Elbasvir) in 10 HCV-negative subjects with heart failure receiving a heart transplant from a HCV-positive donor. Eligible subjects will receive a heart transplant from a deceased-donor with genotype 1 or 4 HCV, and then will receive 12 weeks of Zepatier after heart transplantation when infection with HCV is confirmed in these heart transplant recipients. Treatment will be complete after 12 weeks.*
 
* Patients with Genotype 1a and Genotype 1 with an unknown subtype will have baseline NS5A drug resistance assay testing checked at the start of treatment, and if patients have polymorphisms at positions M28, Q30, L31, and/or Y93, treatment with Zepatier will be extended to 16 weeks, rather than 12 weeks, and renally-adjusted Ribavirin at the clinician's discretion will be initiated, and continued for the remainder of therapy (until the 16 week mark). Such a strategy will provide optimal treatment, without delaying therapy prior to receipt of results of NS5A drug resistant testing.

Study observations	
 • Laboratory tests including hepatic function panel at screening and at multiple time points during follow-up. • HCV RNA prior to treatment, on treatment, and 4 and 12 weeks after completing Zepatier.
Type of control	None

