Number of subjects	Estimated 10 HCV-negative subjects transplanted with a heart from an HCV-positive donor
Plan for statistical analysis	
Primary endpoint:
 
 • Post-treatment sustained virologic response (SVR)

	
Secondary endpoints:
 
• Determine if there are major adverse events attributable to HCV therapy in post-heart transplant patients.• Evaluate 1-year heart graft survival in HCV-negative patients who receive a heart transplant from an HCV-positive donor• Determine the rates of spontaneous HCV clearance among HCV-negative patients with heart failure receiving a heart from an HCV-positive donor 
Data analysis:
 
The primary analysis will be based on a calculation of SVR rates (number of subjects with SVR-12; negative HCV RNA 12 weeks after completing Zepatier therapy) / (number of subjects treated with Zepatier post-heart transplantation)

--	---

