5.2. Specific aims

Primary aim:

1. Primary efficacy objective: To determine sustained virologic response (SVR) rates of open-label Zepatier in hepatitis C virus (HCV) negative patients who receive a heart transplant from a genotype 1 or 4 HCV-positive donor, leading to post-transplantation de-novo HCV infection.
2. Primary safety objective: To determine the safety of administration of open-label Zepatier among HCV-negative patients who receive a heart transplant from a genotype 1 or 4 HCV-positive donor and develop post-transplant HCV infection.

Secondary aim:

1. To determine 1-year graft survival rates of HCV-negative heart transplant patients who receive a heart transplant from a genotype 1 or 4 HCV-positive donor, including those who spontaneously clear HCV and those who receive open-label Zepatier upon development of de-novo HCV.
2. To obtain preliminary data on the distribution of changes in circulating biomarkers of endothelial damage and coronary vasculopathy in HCV-negative patients transplanted with hearts from HCV-positive donors prior to HCV treatment, after viral clearance, and after SVR.
3. To evaluate rates of spontaneous clearance of HCV among HCV-negative patients who receive a heart transplant from a genotype 1 or 4 HCV-positive donor.
4. To identify the viral reservoirs leading to HCV transmission in HCV-negative patients receiving a heart transplant from a HCV-positive donor based on endomyocardial biopsies, measures of HCV antigens in peripheral mononuclear blood cells, and histological examination of arterial and venous tissue surrounding the transplanted heart.
5. To compare the quality-of-life of HCV-negative patients receiving a heart transplant from a HCV-positive donor to those of similar patients remaining on the waitlist for a standard deceased donor heart transplant.

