7.1.1. Administration of study medication

Merck & Co will manufacture, package, and label Zepatier drug. There will be one bottle per subject containing a 28-day supply (28 capsules) of 100/50 mg Zepatier tablets. Daily dose will be one tablet.

The Investigational Drug Services (IDS) pharmacy, directed by [name], will only be required to store and distribute the study drug. Sofosbuvir and Ribavirin will be purchased and sourced locally. Both of these medications will be purchased and stored by the IDS pharmacy at Penn. Ribavirin will be generic and the manufacturer will vary depending on monthly price fluctuations.

Zepatier will be picked up from the investigational drug services (IDS) pharmacy by the research staff at 28-day intervals. The study staff will deliver the medication to the subjects at their study visits (patients expected to be at home by the time that HCV therapy is initiated and patients will be given medication at their scheduled post-transplant/study visit). Treatment with the study drug will begin within 4 weeks post-transplant. If hepatitis C is not cured after a subject has received Zepatier, he or she will be treated with a second regimen that includes Zepatier plus Sovaldi (Sofosbuvir) and Ribavirin. Any patient (male or female) receiving ribavirin as part of the first- or second-line regimen will be required to use two methods of birth control while on Ribavirin therapy, with continuing two forms of birth control for up to 6 months after the last dose of the study drug.

If patients have baseline NS5A drug resistance assay testing that demonstrates polymorphisms at positions M28, Q30, L31, and/or Y93, treatment with Zepatier will be extended to 16 weeks, rather than 12 weeks, and renally-adjusted Ribavirin at the clinician's discretion will be initiated, and continued for the remainder of therapy (until the 16 week mark). Such a strategy will provide optimal treatment, without delaying therapy prior to receipt of results of NS5A drug resistant testing.

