7.1.4. Zepatier Initial Treatment Failures

Study subjects with treatment failure, defined as virologic breakthrough (when an undetectable viral load while on treatment becomes detectable) or virologic relapse (undetectable viral load after completion of treatment that during the 12-week post-treatment follow-up period becomes detectable) will be provided open-label Zepatier + Sofosbuvir (Sovaldi) 400 mg + Ribavirin (generic), renally dosed based on creatinine clearance per the manufacturer guidelines. Any subjects who experience treatment failure will repeat the original study lab visit and visit protocol once they begin their secondary treatment with Zepatier, sofosbuvir, and ribavirin, similar to

subjects initiating HCV treatment following heart transplantation. Prior to initiating treatment with this regimen, patients will have serum NS5A resistance (RAV) testing.

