10 CHAPTER 7: STATISTICAL CONSIDERATIONS

10.1. Study Design

This open-label trial involves one primary and several secondary objectives. Post-transplant HCV status will be monitored, and patients will be treated with 12-16 weeks of Zepatier therapy, after which time, treatment will be complete, barring instances of treatment failure, which would require an additional 12 weeks of therapy.*

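### Primary SVR-12 names no treatment course and has no rule for subjects given second-line therapy, so a rescue cure could be scored as a primary success

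*Combined protocol and SAP*

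**What the plan says.** **The endpoint.** Section 9.1.1 requires undetectable HCV RNA "12 weeks after completing treatment for HCV (12 weeks after the subject takes the last dose of Zepatier". The Synopsis (data analysis) puts in the numerator subjects with "negative HCV RNA 12 weeks after completing Zepatier therapy" and in the denominator all subjects treated with Zepatier after transplant. Neither names a course.

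**The second course.** Section 7.1.4 says that subjects with breakthrough or relapse "will be provided open-label Zepatier + Sofosbuvir (Sovaldi) 400 mg + Ribavirin (generic". Section 7.1.1 words the trigger more broadly, as hepatitis C that is "not cured after a subject has received Zepatier, he or she will be treated with a second regimen that includes Zepatier". Section 8.1.3.11 gives the second course a length of 12 weeks and repeats the visits and laboratory tests.

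**Signs that the initial course is meant.**
- The aim in section 5.2 is "To determine sustained virologic response (SVR) rates of open-label Zepatier in hepatitis C virus (HCV) negative patients".
- The Synopsis says "Treatment will be complete after 12 weeks", with a 16-week exception for resistance polymorphisms.
- The heading of section 7.1.4 refers to initial treatment failures, and its text dates relapse as "undetectable viral load after completion of treatment that during the 12-week post-treatment follow-up period becomes detectable".
- Sections 7.1.1 and 8.1.3.3.1 distinguish first- from second-line regimens, and section 12.10.3 speaks of failing first-line therapy.
- The schedule in section 8.2.1 places SVR 12 at week 24.

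**The analysis text.** Section 10.1 says "patients will be treated with 12-16 weeks of Zepatier therapy, after which time, treatment will be complete, barring instances of treatment failure". Section 10.3 names SVR-12 as the primary analysis but does not say how a subject who fails or receives second-line therapy is scored.

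**The concern.** Because both regimens contain Zepatier, a retreated subject has two candidate dates for the last dose, and the wording of 9.1.1 points to the later one. The exception in 10.1 for treatment failure pulls the same way, since treatment is then not complete until the second course ends. On that reading the primary rate describes Zepatier backed up by sofosbuvir and ribavirin, whereas the stated aim is the SVR rate of Zepatier.

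Choosing the earlier date does not settle the matter. Section 7.1.4 defines failure as the trigger for second-line therapy but does not link it to the primary score. A subject already on second-line therapy when the initial-course sample falls due can have undetectable RNA because of the second regimen and still satisfy 9.1.1.

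At stake is the pilot's main efficacy figure, which section 4.1 expects to lead to a multi-center trial.

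**Working it through.** The plan states no null rate, power, threshold or interval method for this endpoint, so there is no figure of its own to reproduce. The check is of the text first, then of size.

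**Inputs**
- n = 10 treated (Synopsis, section 3).
- First-line SVR p = 94 to 100% (sections 4.3 and 7.1). I use 94%, 97% and 100%; the 97% is my midpoint.
- HCV RNA samples at week 16 (SVR 4), week 20 (SVR 8) and week 24 (SVR 12), from section 8.2.1.
- Second course of 12 weeks (8.1.3.11).

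**Step 1. Timing with the initial-course anchor.** Assume second-line therapy starts in the week failure is found; the resistance testing that 7.1.4 requires first would delay it.
- Relapse found at week 16: second course runs from week 16 to 16 + 12 = 28. The week-24 sample falls 24 − 16 = 8 weeks into it.
- Relapse found at week 20: the week-24 sample falls 24 − 20 = 4 weeks into it.
- Breakthrough with an immediate switch: the last initial-course dose is at the switch, so a sample 12 weeks later falls at the end of the 12-week second course.

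In each case 9.1.1 has no words that stop an undetectable result from counting.

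**Step 2. Timing with the literal anchor.** The second-line SVR-12 falls at (week second-line therapy starts) + 12 + 12.
- On the schedule's own weeks: 16 + 24 = week 40, and 24 + 24 = week 48.
- First dose at week 1 to 4 (8.1.3.3), 12-week course, second-line therapy started 4 to 12 weeks after it ends: earliest 1 + 12 + 4 + 24 = week 41, latest 4 + 12 + 12 + 24 = week 52.
- Same with a 16-week course: week 45 to week 56.

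So the result is available before the week-52 visit only with earlier timing.

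**Step 3. Effect of one subject.** Intervals are exact (Clopper-Pearson), my choice of method. For 10/10 the lower limit is 0.025^(1/10) = 0.692. For 9/10 the upper limit is 0.975^(1/10) = 0.997, and the lower limit solves p^10 + 10p^9(1 − p) = 0.025, giving 0.555.

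| Handling of one first-course failure later undetectable on or after second-line therapy | Rate | 95% CI |
|---|---|---|
| Non-responder | 9/10 = 90% | 55.5 to 99.7 |
| Responder | 10/10 = 100% | 69.2 to 100 |

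Each subject counts once in the denominator, so the shift is 1/10 = 10 points and can only be upward.

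**Step 4. How often it could arise.** P(at least one first-course failure) = 1 − p^10. P(at least two) = 1 − p^10 − 10(1 − p)p^9.

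| First-line SVR | No failure | At least one | At least two |
|---|---|---|---|
| 94% | 53.9% | 46.1% | 11.8% |
| 97% | 73.7% | 26.3% | 3.5% |
| 100% | 100% | 0% | 0% |

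The third column is an upper bound on how often the wording matters. The failure must also be retreated, and the subject must be undetectable at whichever sample is used.

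**The case against.** The strongest reply is that nobody would read the plan literally. Much of this stands. Besides the signs already listed, 10.1 uses Zepatier therapy as the name for the 12- to 16-week course, which makes the Synopsis formula less ambiguous than 9.1.1. A subject reaches second-line therapy only after being classed as a failure or not cured, so counting that subject as a first-line success would contradict the classification. A relapser who is still viremic at the week-12 sample and has not been retreated already fails under 9.1.1 as written. The practical gap is therefore narrow.

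It is not closed, however. Intent settles which course is meant, but not how to score a subject who is on second-line therapy when the initial-course sample is due. Sections 10.4 (completers only) and 10.5 (intention to treat) do not supply that rule either.

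A reader might infer that the plan means to count rescue cures, or that the reported rate will be inflated by a predictable amount. The documents support neither. The intent runs the other way, and no second-line cure rate is given from which an expected inflation could be worked out.

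**Conclusion.** The point holds as a gap in the definition. The initial course is fairly plainly intended, but neither the endpoint wording nor the analysis section secures that estimate, under either choice of last dose. The size is 10 points per affected subject, always upward. The chance that any subject could be affected is at most 46% at a first-line SVR of 94%, 26% at 97% and zero at 100%.

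These chances assume 10 treated subjects with independent outcomes, and that the cited SVR range carries over to heart transplant recipients. The timing in step 1 assumes prompt retreatment. No test or success threshold exists, so no formal decision changes. What is exposed is the reported rate and its interval, and settling the rule before results are known removes a later choice between, for example, 90% and 100%.

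**What to change.** In 9.1.1, 10.3 and the Synopsis:
- Define primary SVR-12 as undetectable HCV RNA 12 weeks after the last dose of the initial Zepatier course, whether 12 or 16 weeks.
- Score as a non-responder any subject who starts second-line HCV therapy before that sample.
- Report any SVR after second-line therapy separately and descriptively, outside the primary numerator. Listing it in 9.2 is optional.

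Keying the rule to the start of second-line therapy covers both the narrower trigger in 7.1.4 and the broader one in 7.1.1. It also avoids overriding an undetectable week-12 result in a subject who met the breakthrough definition but was never retreated.

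The cost is a few sentences, with no new data and no change to sample size or treatment. The downside is that the reported primary rate may be slightly lower.
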